## **8. STUDY INTERVENTION**

### **8.1 Identity of Investigational Products (treatment)**

IMP means intravenous tranexamic acid (1g loading dose given as 100 ml infusion over 10 minutes, followed by another 1g in 250 ml infused over 8 hours) or as comparator placebo (normal saline 0.9%) administered by identical regimen.

#### **8.1.1 Experimental Intervention (treatment)**

IMP means intravenous tranexamic acid (1g loading dose given in 100 ml infusion over 10 minutes, followed by another 1g in 250 ml infused over 8 hours)

#### **8.1.2 Control Intervention (comparator treatment)**

Control intervention means intravenous saline 0.9% (10ml NaCl 0.9% in 100 ml given as loading dose infusion over 10 minutes, followed by another 250 ml NACL 0.9% infused over 8 hours)

#### **8.1.3 Packaging, Labelling and Supply (re-supply)**

The web-based system operates as follows: Participating centres will be allocated a batch of trial treatment. The container numbers for these batches are tracked by the web-based system to the participating site and once receipt has been confirmed they are released for use in the trial. When the supplies at the participating centre reach a pre-determined level then a re-order is triggered and a further supply of trial treatment is sent to the corresponding participating site.

#### **8.1.4 Storage Conditions, dispense and return**

The packs will be stored at room temperature and protected from excessive heat and freezing in a restricted access area. Stability data exists which demonstrates that Tranexamic Acid is stable at temperatures between -20°C and 50°C. Temperature monitoring will not be required. The IMP will be clearly labelled for clinical trial use only. Each pack will be a numbered box containing either tranexamic acid or placebo according to a computer-defined sequence.

The local site investigator is responsible for ensuring trial treatment accountability, including reconciliation of trial treatment and maintenance of trial treatment records, throughout the course of the study in accordance with local regulatory requirements. Responsibility can be delegated to the site pharmacy clinical trials staff.

Following randomisation the participant will be allocated a treatment pack number. Specifically authorised personnel will retrieve the appropriate pack number and complete the participant name, date of randomisation and participant number. Pack number allocation will be checked and countersigned by the research staff and the nursing staff administering the treatment. The treatment will be prescribed on the participant's treatment chart as trial medication. The nurse administering the study treatment is unblinded, which represents a potential bias. Nevertheless, all personal will receive order not to communicate to anybody the treatment and whether it contains tranexamic acid or placebo. Nursing staff administering the treatment is not involved in the evaluation of any outcome parameters.

Dispensing will be recorded on the appropriate trial specific accountability forms. Trial treatment must not be used for any other purpose than the present study. Returned trial treatment that has been dispensed to a participant must not be re-dispensed to a different participant. Any unused drug will be returned to pharmacy.

### **8.2 Compliance with study intervention**

Compliance with study intervention will be monitored by checking prescription drug charts. The pharmacist will maintain records of the dispensing of the drug and the research nurse will record administration of the drug to the patient. Dispensing details will be recorded on each participant's CRF. Unused and partially used supplies will be returned to pharmacy. This will be recorded in the pharmacy study log.

## 9. STUDY ASSESSMENTS

Participants will be assessed before treatment (day 1), after treatment (day 2), after 7 days, at death/discharge and 90 days. See flow chart for more details.

Patients will be assessed clinically at baseline in line with local clinical practice prior to inclusion (day 1), end of treatment (day 2), on day 7 and at discharge/death (in hospital – if death/discharge occurs before day 7 visit, both visits are performed simultaneously). Follow up at day 90 (+/- 14 days) will be via a clinical outpatient visit or – if the patients' functional status does not allow outpatient visit – by a structured telephone interview with the patient, next-to-kin or other care-giver.

Brain imaging (CT head scan) will be performed as part of routine clinical management prior to enrolment (all acute stroke patients have a CT head scan performed on admission to hospital). For the purpose of the study the CT head scan will be repeated after treatment, day 2, (tranexamic acid/placebo) to assess haematoma expansion. A day 2 CT scan for patients with intracerebral haemorrhage is part of standard care in many stroke centers. In this case, routine day 2 CT scan can be used for trial purpose and no additional CT scan is required. If a patient received MRI scan on admission as first neuroimaging, the patient will undergo a baseline CT scan after inclusion in the trial to assure that hematoma expansion can be measured correctly and is comparable throughout all patients included in the study.

### 9.1 Study flow chart(s) / table of study procedures and assessments

Study Periods	Screening	Randomisation /Treatment	Follow-up			
			3	4	5	6
Visit	1	2	3	4	5	6
day	1	1	2	7 (+/- 24h)	Death/ discharge	90 (+/- 14 days)
Patient Information and Informed Consent	x					
Demographics	x					
Medical History	x					
In- /Exclusion Criteria	x					
NIHSS	x		x	x		x
Vital Signs (RR, heart rate)	x		x	x		x
Laboratory Tests	x*					
Pregnancy Test#	x					
Randomisation		x				
CT scan	x*	x 	x			
Study treatment		x				
mRS	x		x	x	x	x
Secondary outcome variables						x
Concomitant Therapy, Intervention		x	x	x	x	
Adverse Events		x	x	x	x	x

NIHSS: National Institute of Health Stroke Severity Scale; mRS: modified Rankin Scale Score; CT: computer tomography

\* routine CT scan/laboratory test

# in woman of childbearing age

1only if no baseline-CT scan performed as part of routine-work up (for example baseline brain imaging

is MRI)

## 9.2 Assessments of outcomes

### 9.2.1 Assessment of primary outcome

Evaluation of hematoma volume and hematoma expansion will be based on 2 CT scans. All participants at one center will be evaluated with identical imaging protocols at baseline and follow-up. The first CT scan is part of clinical routine. The follow-up scan on day 2 will be part of the study protocol (if not performed in routine clinical care). If a patient received MRI scan on admission as first neuroimaging, the patient will undergo a baseline CT scan after inclusion in the trial to assure that hematoma expansion can be measured correctly and is comparable throughout all patients included in the study.

In line with prior research, hematoma expansion (HE) is defined as an increase of 33% relative or 6ml absolute growth between ICH-volume on baseline CT and on follow-up-CT at  $24 \pm 3$  hours.

All images will be evaluated independently by a rater blinded to treatment and outcome (experienced stroke neurologist/neuroradiologist) at the imaging core lab in Basel.

Any intraventricular hemorrhage (IVH) components will not be included in ICH volumes. In addition, presence or absence of the spot-sign on baseline CT-scan will be assessed in the core lab.

Semi-automatic segmentation by region growing will be performed using the Aquarius software (Version 4.4.8) by Terarecon. The target region (hematoma) will be selected manually and region growing in full resolution and medium connectivity will be done automatically (region growing is spherical from seed point with regard to hounsfield units connected to seed point). Finally, segmentation and identified hematoma in three planes will be controlled manually. Target volumetry will be calculated automatically of the segmented area by the software and will result in a volume given in cm^3.

### 9.2.2 Assessment of secondary outcomes

The following secondary outcome measures are assessed at day 90 and day 365 visit: (I) modified Rankin Scale (mRS) 0–4; (II) mRS 0–3; (III) Categorical shift in mRS; (IV) Death due to any cause.

The following secondary outcome measures are assessed based on the day 2 CT-scan: (V) Absolute ICH growth volume by  $24 \pm 3$  hours, adjusted for baseline ICH volume; (VI) Symptomatic HE defined as HE and neurological deterioration of NIHSS >4 points or GCS >2 points

### 9.2.3 Assessment of safety outcomes

Throughout the study, information on the following safety outcome events will be collected at each visit: major thromboembolic events (myocardial infarction, ischemic stroke, pulmonary embolism)

#### 9.2.3.1 Adverse events

An adverse event is any unfavourable and unintended sign, symptom, syndrome or illness that develops or worsens during the period of observation in the study.

An AE does include a / an:

1. Exacerbation of a pre-existing illness.
2. Increase in frequency or intensity of a pre-existing episodic event or condition.
3. Condition detected or diagnosed after medicinal product administration even though it may have been present prior to the start of the study.
4. Continuous persistent disease or symptoms present at baseline that worsen following the start of the study.

An AE does not include a / an:

1. Medical or surgical procedure (e.g., surgery, endoscopy, tooth extraction, transfusion); but the condition that lead to the procedure is an AE.
2. Pre-existing disease or conditions present or detected at the start of the study that did not worsen.
3. Situations where an untoward medical occurrence has not occurred (e.g., hospitalisations for cosmetic elective surgery, social and / or convenience admissions).

4. Disease or disorder being studied or sign or symptom associated with the disease or disorder unless more severe than expected for the participant's condition.
5. Overdose of concurrent medication without any signs or symptoms.

A Serious Adverse Event (SAE) is any adverse event occurring following study mandated procedures, having received the IMP or placebo that results in any of the following outcomes:

1. Death
2. A life-threatening adverse event
3. Inpatient hospitalisation or prolongation of existing hospitalisation
4. A disability / incapacity
5. A congenital anomaly in the offspring of a participant

Important medical events that may not result in death, be life-threatening, or require hospitalisation may be considered a serious adverse event when, based upon appropriate medical judgment, they may jeopardize the patient or participant and may require medical or surgical intervention to prevent one of the outcomes listed in this definition.

A distinction is drawn between serious and severe AEs. Severity is a measure of intensity whereas seriousness is defined using the criteria above. Hence, a severe AE need not necessarily be serious. Serious adverse events are common in haemorrhagic stroke, for a full list of expected SAE that are not subject to expedited reporting, investigators should refer to Appendix A.

As the IMP is administered once and has a short half-life, serious adverse events occurring within the first 7 days will be assessed for seriousness, expectedness and causality. In addition fatal SAEs and safety outcome events (VTE, recurrent stroke, TIA, MI, PAD and seizures) will be reported until day 90.

#### **9.2.4 Causality and reporting**

**Not related or improbable:** a clinical event including laboratory test abnormality with temporal relationship to trial treatment administration which makes a causal relationship incompatible or for which other drugs, chemicals or disease provide a plausible explanation. This will be counted as “unrelated” for notification purposes.

**Possible:** a clinical event, including laboratory test abnormality, with temporal relationship to trial treatment administration which makes a causal relationship a reasonable possibility, but which could also be explained by other drugs, chemicals or concurrent disease. This will be counted as “related” for notification purposes.

**Probable:** a clinical event, including laboratory test abnormality, with temporal relationship to trial treatment administration which makes a causal relationship a reasonable possibility, and is unlikely to be due to other drugs, chemicals or concurrent disease. This will be counted as “related” for notification purposes.

**Definite:** a clinical event, including laboratory test abnormality, with temporal relationship to trial treatment administration which makes a causal relationship a reasonable possibility, and which can definitely not be attributed to other causes. This will be counted as “related” for notification purposes.

An AE whose causal relationship to the study IMP is assessed by the Chief Investigator as “possible”, “probable”, or “definite” is an Adverse Drug Reaction. With regard to the criteria above, medical and scientific judgment shall be used in deciding whether prompt reporting is appropriate in that situation.

Participants will be asked to contact the study site immediately in the event of any serious adverse event. All adverse events will be recorded and closely monitored until resolution, stabilisation, or until it has been shown that the study medication or treatment is not the cause. The Chief Investigator (delegated the sponsor's responsibilities) shall be informed immediately (within 24 hours) of any serious adverse events, occurring within the first 7 days and shall determine seriousness and causality in conjunction with any treating medical practitioners. Reporting of SAE to the competent EC will be done in accordance with Swiss laws.

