## **3.3 Explanation for choice of comparator (or placebo)**

The comparator of the IMP is placebo in addition to best medical treatment in a Stroke Center according to local SOPs following national and international guidelines. The trial steering committee encourages all investigators to evaluate the use of idaruzicumab for patients suffering ICH under dabigatran or andexanet alpha for patients suffering ICH under treatment with a factor Xa-inhibitor (edoxaban, rivaroxaban or edoxaban) if available. This approach guaranties that NOAC-ICH-patients participating on TICH-NOAC will have the chance to benefit from a potentially beneficial agent on top of state-of-the-art treatment, available for all participants.

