### Risks:

Patients may experience an increased risk for thromboembolic complications including ischemic stroke or deep venous thrombosis due to treatment with tranexamic acid although this risk was not elevated compared to placebo in prior trials involving tranexamic acid.

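### The causality scale in section 9.2.4 lets one event meet both an unrelated and a related category, with no rule for which prevails

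*Combined protocol and SAP*

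**What the plan says.** Section 9.2.4 sets out four causality categories. Two matter here.

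- *Not related or improbable*: an event whose temporal relationship to treatment is one "which makes a causal relationship incompatible or for which other drugs, chemicals or disease provide a plausible explanation". The consequence is: "This will be counted as “unrelated” for notification purposes".
- *Possible*: an event with a temporal relationship "which makes a causal relationship a reasonable possibility, but which could also be explained by other drugs, chemicals or concurrent disease". The consequence is the opposite: "This will be counted as “related” for notification purposes".

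*Probable* and *Definite* also count as related. They apply when other causes are unlikely or excluded.

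The category then decides drug-reaction status: an adverse event "assessed by the Chief Investigator as “possible”, “probable”, or “definite” is an Adverse Drug Reaction". The same section calls for medical and scientific judgment, but only on whether prompt reporting is appropriate. It does not say which category takes precedence when two fit.

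**The concern.** A causality scale should send each event to one category. Here the first two overlap, and they lead to opposite results for notification.

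The overlap touches the risk that the protocol itself puts first. Section 3.4 states: "Patients may experience an increased risk for thromboembolic complications including ischemic stroke or deep venous thrombosis due to treatment with tranexamic acid". Section 3.1 describes NOACs as used for stroke prevention in atrial fibrillation and for venous thrombosis and pulmonary embolism, so participants carry an underlying reason to form clots. Section 3.3 adds possible other drugs: "The trial steering committee encourages all investigators to evaluate the use of idaruzicumab" in dabigatran-related bleeding, and makes a parallel suggestion for factor Xa inhibitors. An ischaemic stroke or pulmonary embolism a few days after the infusion can thus have compatible timing and a plausible alternative cause at once.

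At stake is whether such an event enters the Adverse Drug Reaction count and, if it is serious and unexpected, the SUSAR route in section 10.1.2 (7 days if fatal, 15 days otherwise).

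**Working it through.** No arithmetic applies. The check sets the definitions side by side and follows the category through to its consequences.

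**Step 1. Definitions in logical form.** Inputs: the category texts in section 9.2.4. Let I = timing incompatible with a causal link, T = timing makes a causal link reasonably possible, and A = another drug, chemical or disease plausibly explains the event. I and T exclude each other.

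- *Not related or improbable* = I or A
- *Possible* = T and A

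**Step 2. Go through the cases.**

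| Timing | Plausible alternative | Category met as written | Status |
|---|---|---|---|
| Incompatible | yes | Not related | unrelated |
| Incompatible | no | Not related | unrelated |
| Reasonable | no | Probable or Definite | related |
| Reasonable | yes | Not related **and** Possible | unrelated **and** related |

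Whenever T and A both hold, A alone already satisfies the first definition. If the wording in *Possible* about an event that could also be explained otherwise is taken to mean a plausible explanation, the whole of *Possible* lies inside *Not related*. If it is taken as a weaker condition, the overlap is confined to events with a plausible alternative. Either way it is not empty.

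**Step 3. Look for a tie-break.** Section 9.2.4 has no order of precedence and no default to the more cautious category. The judgment clause concerns prompt reporting, not classification.

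**Step 4. Follow the consequence.** Under section 9.2.4 only *Possible*, *Probable* and *Definite* events are Adverse Drug Reactions. The abbreviation list spells out SUSAR as a suspected, unexpected, serious adverse reaction, so the duty in section 10.1.2 cannot arise for an event held to be unrelated. Section 9.2.3.1 limits the formal assessment of SAE causality to the first 7 days, so for SAEs the overlap operates in that window.

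**Step 5. Check what does not depend on causality.**

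- Section 9.2.3: major thromboembolic events are collected at each visit.
- Section 9.2.3.1: fatal SAEs and safety outcome events are reported to day 90.
- Section 10.1.1: all SAEs go to the Sponsor-Investigator within 24 hours.
- Section 11.3: evidence of hazard includes VTE and ischaemic events.
- Section 12.2: the DSMB reviews SAEs after 50% and 80% of recruitment.

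None of these uses the causality category.

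**The case against.** Four arguments can be made for the plan.

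*The ordinary reading is clear enough.* The label of the first category and the four-step ladder suggest that its alternative cause is meant to be one that makes the drug improbable, as against one that merely might also explain the event. That is probably the intention, but the text does not say it. Applied as written, the second condition needs no judgment that the drug is improbable.

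*Classification is central.* A reader might infer that two sites could give the same event opposite drug-reaction status. The documents do not support this. Section 9.2.4 has the Chief Investigator determine causality together with the treating practitioners, and section 10.1.1 has the Sponsor-Investigator re-evaluate each SAE. This objection stands against the claim about sites. It does not remove the contradiction, because the central assessor works from the same definitions.

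*Thromboembolic events may not be SUSARs in any case.* A SUSAR must be unexpected. Section 3.2.6 lists rare thromboembolic events among the known side effects. Section 10.1.1 allows exemption from expedited reporting for SAEs that are well known and described in the product information, and section 9.2.3.1 refers to Appendix A for expected SAEs. Appendix A is not in the text available for this review. This objection stands in part: the size of any SUSAR effect is open.

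*The main harm is monitored without regard to causality.* This stands in full, for the reasons in the last step of the check.

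**Conclusion.** The causality scale is wrong as written. An event with reasonable timing and a plausible alternative cause is both unrelated and related for notification, and the protocol does not say which prevails. The text therefore allows early thromboembolic events to be left out of the Adverse Drug Reaction count and, where they are also serious and unexpected, out of SUSAR reporting.

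The size can only be described in words. That many early thromboembolic events will have an alternative explanation is an inference from the NOAC indications in section 3.1 and the possible antidote use in section 3.3; the documents give no rate. It also assumes that those events occur with compatible timing.

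Three stronger conclusions are tempting and are not supported:

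- That nearly all such events would be filed as unrelated. The text permits this, but nothing shows that it would be done.
- That SUSAR reporting of thromboembolism is lost. This depends on expectedness, which cannot be settled here.
- That the safety comparison between arms or the DSMB review is compromised. Neither uses the causality category.

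**What to change.** Amend section 9.2.4, and the SAE form if it repeats the scale, as follows.

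- Keep incompatible timing sufficient by itself for *Not related or improbable*.
- Limit the second condition to events whose timing makes a causal link improbable **and** for which another drug, chemical or disease is a plausible explanation.
- Add a precedence sentence, for example: *An alternative explanation alone does not make an event unrelated; if the timing leaves a causal link reasonably possible, the event is classified at least as Possible.*

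Simply replacing *or* by *and* in the first category would not do. An event with incompatible timing and no identified alternative cause would then fit no category: it would fail the first for want of an alternative, and the other three because they require reasonable timing.

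The cost is a short edit that leaves endpoints, sample size and analysis unchanged. The downside is that somewhat more events will be counted as related and reported.

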## 10. SAFETY

During hospitalisation in the participating center until day 7, all adverse events (AE) and all serious adverse events (SAEs) are collected, fully investigated and documented in source documents and case report forms (CRF). After discharge from the participating hospital and/or day 7 (what occurs first), only study outcome events (death, ischemic vascular events) are collected as SAE until end of study. Study duration encompassed the time from when the participant signs the informed consent until the last protocol-specific procedure has been completed.

